- Evaluate the proportion of patients achieving clinical response and biochemical response (fecal calprotectin [FC] and C-reactive protein [CRP]) at Weeks 12, 24, and 54.
- Measure improvement in patient-reported outcomes (PROs), including the urgency numeric scale (UNRS), at Weeks 12, 24, and 54.
- Assess mucosal and histological healing at Week 54 using endoscopy and biopsy.
- Evaluate changes in rectal and colonic wall thickness via ultrasound, if feasible[6].

Endpoints

Composite Endpoint:

Proportion of patients achieving deep remission at 54 ± 4 weeks, defined as: Mayo rectal bleeding subscore = 0, stool frequency subscore = 0, endoscopic subscore ≤ 1 .

Secondary Endpoints:

- Proportion of patients achieving clinical response at Weeks 12, 24, and 54, defined as
 a decrease from baseline in Mayo Clinic total score of ≥3 points and ≥30%, with a
 decrease in rectal bleeding subscore of ≥1 or an absolute rectal bleeding subscore of
 0 or 1.
- Change from baseline in PRO scores, including the urgency numeric scale (UNRS), at Weeks 12, 24, and 54.
- Proportion of patients achieving biochemical response (normalization or significant reduction in FC and CRP levels) at Weeks 12, 24, and 54.
- Safety outcomes: Incidence and severity of adverse events (AEs), serious adverse events (SAEs), and discontinuations due to AEs throughout the study.

Outcomes measurement

Primary Outcome Measures:

1. Clinical Remission at 24 and 54 ± 4 weeks

 \circ To assess the proportion of patients achieving clinical remission at 54 ± 4 weeks, defined as a modified Mayo score (MMS) with a rectal bleeding subscore of 0, stool frequency subscore of 0 or 1 with at least a 1-point reduction from baseline, and an endoscopic subscore of 0 or 1 (excluding friability).

Secondary Outcome Measures:

1. Endoscopic Remission at 54 ± 4 weeks

To determine the proportion of patients attaining endoscopic remission at 54 ± 4 weeks, defined as a Mayo endoscopic subscore of 0 or 1 (excluding friability) and UCEIS score.

2. Histologic Remission at 54 ± 4 weeks

o To evaluate histologic remission at 54 ± 4 weeks using the Nancy histological score. Remission is defined as a Nancy histological score of 0.

3. Symptomatic Remission at 12, 24 e 54 ± 4 weeks

To assess the proportion of patients achieving symptomatic remission at 12,
 24 e 54 ± 4 weeks, defined as a Mayo score with a rectal bleeding subscore of
 0 and a stool frequency subscore of 0 or 1 with at least a 1-point decrease

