• To evaluate the proportion of patients achieving disease clearance at 12, 24 e 54 \pm 4 weeks, defined as simultaneous attainment of deep remission (see above) and histologic remission (Nancy Histological Index = 0, indicating absence of significant inflammatory infiltrate)

13. Quality of Life Assessment

- To assess changes in health-related quality of life, measured using the IBD Disability Index (IBD-Disk) and the Functional Assessment of Chronic Illness Therapy–Fatigue (FACIT–Fatigue) questionnaire, 12, 24 e 54 ± 4 weeks.
- 14. Safety assessment through the 54 weeks, reporting side effects related to Etrasimod

Study Population

Inclusion Criteria:

- Adults aged ≥18 years with a confirmed diagnosis of UC for at least 6 months.
- Moderate-to-severe UC defined by a Mayo Clinic total score between 6 and 12 inclusive, with an endoscopic subscore ≥2.
- Inadequate response, loss of response, or intolerance to at least one prior biologic therapy (e.g., anti-TNF agents, vedolizumab, ustekinumab).

Exclusion Criteria:

- Diagnosis of Crohn's disease or indeterminate colitis.
- History of colectomy or anticipated need for colectomy during the study period.
- Presence of colonic dysplasia or malignancy.
- Active or latent tuberculosis not adequately treated.
- Serious uncontrolled medical conditions (e.g., severe infection, significant hepatic or renal impairment).
- Known hypersensitivity to Etrasimod or its excipients.

Intervention

Etrasimod Dosing Regimen:

- Induction Phase:
 - Etrasimod 2 mg administered orally once daily.

Maintenance Phase:

• Etrasimod 2 mg administered orally once daily up to Week 54.

Study Assessments and Visits

Baseline (Week 0):

- Comprehensive clinical assessment, including 9-point MMS.
- Endoscopic evaluation to assess mucosal appearance (endoscopic MAYO and UCEIS scores).
- Histological assessment via biopsy (Nancy score).
- Baseline PROs, including urgency numeric scale (UNRS).
- Laboratory tests: FC, CRP, complete blood count (CBC), liver and renal function tests.
- Collection of demographic and disease-specific data.
- Ultrasound evaluation of colonic and rectal wall thickness, if feasible (Milan Ultrasound Criteria).

Week 12, 24, 54 Assessments:

- Clinical response and remission assessment.
- Laboratory tests: FC, CRP.
- PRO assessments, including UNRS.
- Endoscopic and histological evaluation at Week 54.
- Safety monitoring.
- Ultrasound evaluation (Week 54, if feasible).

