Urgency Numeric Rating Scale (UNRS) Assessment:

- Urgency severity will be evaluated using the validated UNRS, with scores ranging from 0 (no urgency) to 10 (worst possible urgency).
- Improvement in UNRS scores will be analyzed at Weeks 12, 24, and 54, and correlated with clinical remission and mucosal healing.
- This assessment will provide insights into symptom control and quality of life improvements in Etrasimod-treated patients.

Safety Monitoring

- Adverse events will be recorded and graded according to the Common Terminology Criteria for Adverse Events (CTCAE) version 5.0.
- Immediate reporting of any serious adverse events to relevant regulatory bodies.

Sample Size Determination:

The required sample size for McNemar's test of paired proportions, based on the asymptotic approximation by Miettinen (1968), with a two-sided alpha level of 0.05, power of 0.8, probabilities of discordant pairs 0–1 and 1–0 equal to 0.35 and 0.10 respectively [10], and a drop-out rate of 5%, is 68 pairs. The McNemar test will be used to assess changes in paired proportions, particularly in the context of pre- and post-intervention comparisons of binary outcomes.

Data Collection

Statistical analysis

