Continuous data will be expressed as mean ± standard deviation (SD) or median and interquartile range (25th-75th percentile), while categorical variables will be reported as absolute and relative frequencies. Normality will be assessed using the Kolmogorov-Smirnov test and Levene's test for homogeneity of variance. The primary endpoint is the proportion of patients achieving deep remission at Week 54, defined as a binary variable. To compare paired proportions (e.g., remission status at baseline vs Week 54), McNemar's test will be used. To identify predictors of remission, multivariable logistic regression models will be applied, adjusting for baseline covariates. Repeated measures at Weeks 12, 24, and 54 will be analyzed using generalized estimating equations (GEE) with an appropriate link function (logit for binary outcomes; identity for continuous) to account for within-subject correlations over time. When evaluating continuous outcomes, repeated-measures ANOVA or linear mixed models may be used as appropriate. Between-group comparisons of continuous variables will be conducted using Student's t-test or Mann-Whitney U test, depending on data distribution. Chi-square or Fisher's exact test will be used for categorical comparisons. Associations between variables will be assessed using Spearman's correlation coefficient. Survival outcomes (if any) will be analyzed using the Kaplan-Meier method, with comparisons made using the log-rank test. Hazard ratios (HR) will also be presented using smoothed estimates to visualize changes over time. A two-tailed p-value < 0.05 will be considered statistically significant. All analyses will be conducted using SPSS v27.0, R (version 3.4.3), and EZR.

Ethical Considerations

- The study will adhere to the Declaration of Helsinki and Good Clinical Practice (GCP) guidelines.
- Written informed consent will be obtained from all participants before any studyrelated procedures.

Enrollment Period

 Duration: Enrollment is planned to commence in July 2025 or upon commercial availability of the investigational drug, which is currently accessible exclusively under compassionate use. The enrollment window will extend for 6 months from the date of drug availability. Each participant will be followed for 54 ± 4 weeks from the time of inclusion.

Recruitment Strategy:

- Patients will be recruited from multiple specialized inflammatory bowel disease (IBD) centers across different geographic regions.

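### The only named McNemar comparison, remission at baseline against Week 54, has an empty cell by eligibility, so the assumed 0.10 discordance and 80% power cannot apply and the test says nothing about effectiveness

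*Protocol*

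**What the plan says.** The Statistical analysis section defines the endpoint: "The primary endpoint is the proportion of patients achieving deep remission at Week 54, defined as a binary variable". The next sentence gives the test and its only example: "To compare paired proportions (e.g., remission status at baseline vs Week 54), McNemar's test will be used".

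Sample Size Determination rests wholly on McNemar's test, "with a two-sided alpha level of 0.05, power of 0.8", with 0–1 and 1–0 discordant probabilities of 0.35 and 0.10 and 5% drop-out, giving 68 pairs. It adds: "The McNemar test will be used to assess changes in paired proportions, particularly in the context of pre- and post-intervention comparisons of binary outcomes". It does not name the outcome to which 0.35 and 0.10 belong. The Protocol gives no comparator, benchmark rate or null value for the Week 54 proportion.

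The Inclusion Criteria admit patients with a "Mayo Clinic total score between 6 and 12 inclusive, with an endoscopic subscore ≥2". Under Endpoints, deep remission is "Mayo rectal bleeding subscore = 0, stool frequency subscore = 0, endoscopic subscore ≤ 1". Under Outcomes measurement, clinical remission (listed there as the primary outcome) and endoscopic remission also need an endoscopic subscore of 0 or 1.

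**The concern.** A before–after test of a binary status is informative only if patients can hold either status before treatment. Here the entry criterion and the remission definitions exclude each other on the endoscopic subscore, so baseline remission is zero for every eligible patient.

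Two things are at stake. First, the sample size rests on a discordance pattern that cannot occur for the endpoint it appears to serve, so the stated power does not describe the planned comparison. Second, in an open-label study without a control arm, a small p-value from this test could be reported as evidence of effectiveness when it shows only that some patients were in remission at Week 54.

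**Working it through.** **Inputs.** From Sample Size Determination: p01 = 0.35, p10 = 0.10, two-sided alpha 0.05, power 0.80, drop-out 5%, N = 68. Evaluable: 68 × 0.95 = 64.6, taken as 64. From Inclusion Criteria: endoscopic subscore ≥2. From Endpoints and Outcomes measurement: remission needs ≤1.

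**The stated sample size.** Let psi = p01 + p10 = 0.45 and d = p01 − p10 = 0.25.
- Miettinen's second-order formula, [1.96·psi + 0.8416·√(psi² − d²(3+psi)/4)]² / (psi·d²), gives 51.7, so 52 pairs; 51.7/0.95 = 54.5, so 55 with drop-out.
- The simple form, (1.96 + 0.8416)²·psi/d², gives 56.5, so 57 pairs and 60 with drop-out.
- The simple form with continuity correction, n/4·[1 + √(1 + 4/(n·d))]², gives 64.3; 64.3/0.95 = 67.6, so 68.

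The stated 68 is thus reached with a continuity correction that the Protocol does not mention. The main point does not depend on this.

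**Baseline status.** The endoscopic criterion alone settles it. Rectal bleeding 0 and stool frequency 0 are arithmetically possible at a total score of 6, but an endoscopic subscore of at least 2 rules out deep, clinical and endoscopic remission. So p10 = 0 for all three, not 0.10.

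**What the test becomes.** Let b be the number of Week 54 remitters and c = 0 the number who lose remission.
- Uncorrected: chi-square = (b − c)²/(b + c) = b. At b = 3, p = 0.083; at b = 4, p = 0.0455.
- Exact: p = 2 × 0.5^b. At b = 5, p = 0.0625; at b = 6, p = 0.031.
- Continuity-corrected: (6 − 1)²/6 = 4.17, p = 0.041 at b = 6.

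Significance therefore needs 4/64 = 6.3% or 6/64 = 9.4% in remission.

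**Probability of significance with n = 64** (binomial upper tail):

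| True Week 54 rate | Uncorrected (≥4) | Exact (≥6) |
|---|---|---|
| 5% | 0.40 | 0.10 |
| 10% | 0.89 | 0.63 |
| 15% | 0.99 | 0.93 |
| 25% | >0.999 | >0.999 |
| 35% | >0.999 | >0.999 |

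With the 1–0 cell empty, the 0–1 probability is itself the Week 54 remission rate, so the 35% row is the Protocol's own assumption and the 25% row its assumed net difference. At 35%, 80% power would need only 15 pairs (uncorrected) or 22 (exact). With 64 patients, 80% power is already reached at a true rate of about 8.5% (uncorrected) or 12% (exact).

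**What the sample does support.** For 22/64 = 34.4% the exact 95% interval is 22.9% to 47.3% (Wilson 23.9% to 46.6%). For 24/68 = 35.3% it is 24.1% to 47.8% (Wilson 25.0% to 47.2%).

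**The case against.** The best defence is that no sentence calls McNemar the primary analysis. The endpoint is defined as a proportion, categorical variables are to be reported as frequencies, and the baseline comparison is introduced only as an example. The 0.35 and 0.10 are not tied to any named outcome, and their cited source is not available here. So a reader might infer that McNemar is the declared primary test, but the documents do not go that far. What they do show is enough: McNemar is the only basis for the sample size, remission at baseline against Week 54 is its only example, and no other outcome is offered to which 0.10 could apply. Another pair of visits does not rescue it, because the visit schedule places endoscopy only at baseline and Week 54.

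Three further readings go too far.
- *That a significant result is guaranteed.* At a true rate of 5% the probability is only 0.10 to 0.40; it is near certain from about 15% upward.
- *That every secondary outcome is affected.* Clinical and endoscopic response are changes from baseline and have no baseline status; the ultrasound outcomes are optional, with no test assigned; symptomatic remission has no endoscopic component. The Protocol states no baseline McNemar test for any of these.
- *That McNemar is invalid throughout.* It remains usable where entry does not fix the status, such as normal CRP or fecal calprotectin.

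It is also fair to say that the error does not leave the study short of patients for the stated test: the true power is above 80%, and the Week 54 proportion stays estimable.

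**Conclusion.** The point stands for deep, clinical and endoscopic remission. For these, the 1–0 probability of 0.10 contradicts the entry criterion, and the 80% power does not describe the only comparison named. The test can be computed but is uninformative about effectiveness: its null is a remission rate of zero, which 4 to 6 remitters among about 64 patients reject.

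The contradiction needs no outside source. The probabilities of significance assume 64 evaluable patients, all meeting the endoscopic entry criterion. The conclusion is the same whether deep or clinical remission is taken as primary. It should be corrected before analysis, because it concerns the sample-size rationale and the only test attached to the primary endpoint.

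**What to change.** In Statistical analysis, state that McNemar's test will not be used for remission endpoints with an endoscopic component, and keep it only for named outcomes that entry does not fix. Make the primary analysis the Week 54 deep-remission proportion with an exact (Clopper-Pearson) or Wilson 95% confidence interval.

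In Sample Size Determination, replace the power statement by precision on one stated denominator: either evaluable patients (22/64, exact interval 22.9% to 47.3%) or all enrolled patients with drop-outs counted as non-remitters (24/68, 24.1% to 47.8%).

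If a test is wanted, use an exact one-sample binomial test against a justified, pre-specified benchmark, with alpha stated. As an illustration only, take an assumed benchmark of 20% (not in the Protocol), a true rate of 35% and an upper tail of 0.025. Power is then 0.775 with 64 patients (reject at 20 or more remitters) and 0.798 with 68 (21 or more). With 64 patients it would be 0.97 against 15% and 0.38 against 25%, so the benchmark needs a real justification.

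The cost is rewording two paragraphs. No patients, visits or data are added. What is lost is a near-automatic significant p-value.

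### About 23 expected remissions are too few for standard maximum-likelihood logistic regression; Firth penalisation would remove most of the bias in the predictor odds ratios at little cost

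*Protocol*

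**What the plan says.** The Statistical analysis section of the Protocol states that, to identify predictors of remission, "multivariable logistic regression models will be applied, adjusting for baseline covariates". The same section sets a two-tailed p-value below 0.05 as the criterion for statistical significance and makes no separate provision for this model. It names R among the packages. It does not give the estimator, the covariates, their number or a selection rule.

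The section defines the outcome as follows: "The primary endpoint is the proportion of patients achieving deep remission at Week 54, defined as a binary variable".

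No expected number of remissions is stated. The inputs that imply one are under Sample Size Determination: "probabilities of discordant pairs 0–1 and 1–0 equal to 0.35 and 0.10 respectively" and "a drop-out rate of 5%, is 68 pairs". Under Study Population, entry requires moderate-to-severe disease "with an endoscopic subscore ≥2".

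The Baseline (Week 0) list under Study Assessments and Visits shows which covariates could be used: the 9-point modified Mayo score, endoscopic Mayo, UCEIS, Nancy score, urgency scale, FC, CRP, blood count, liver and renal tests, ultrasound if feasible, and "Collection of demographic and disease-specific data".

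**The concern.** Logistic regression named without qualification is normally taken to mean maximum likelihood. In small samples with few events, its coefficients are biased away from zero, so odds ratios look stronger than they are, and the bias grows with each added term. The study is sized for a paired comparison of proportions, not for a prediction model. Its event count should therefore be compared with the model before the estimator is settled.

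At stake is how far the reported predictors can be trusted. Inflated odds ratios would overstate how well baseline features separate patients who remit from those who do not. If many features are tested at 0.05, one or more chance findings become likely. The primary result is not affected.

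**Working it through.** **1. The plan's own sample size.** Inputs: two-sided alpha 0.05, power 0.80, p01 = 0.35, p10 = 0.10, so ψ = 0.35 + 0.10 = 0.45 and D = 0.35 − 0.10 = 0.25. Miettinen's formula:

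n = [z(α/2)·ψ + z(β)·√(ψ² − D²(3+ψ)/4)]² / (ψD²)
= [1.960 × 0.45 + 0.842 × √(0.2025 − 0.0539)]² / (0.45 × 0.0625) = 51.7, so 52.

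52 / 0.95 = 54.7, so 55. The stated 68 is not reproduced. That is a separate matter. The stated 68 is used below because it is the planned enrolment and the more favourable figure for the predictor model.

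**2. Expected remissions.** 68 × 0.95 = 64.6, about 65 evaluable. Entry requires an endoscopic subscore of at least 2 and deep remission requires at most 1, so no patient is in remission at baseline. Every Week 54 remission therefore falls in the 0–1 cell.

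- Rate 0.35: 0.35 × 65 = 22.75, about 23 (23.8 if all 68 are analysed).
- Rate 0.25 (taking the net change as the rate): 0.25 × 65 = 16.25, about 16.

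**3. Events per covariate at 22.75 events.** 7.6 with 3 covariates, 4.5 with 5, 2.8 with 8, 2.3 with 10.

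**4. Simulation of the estimators.** Assumptions: n = 65; k independent standard-normal covariates; one true predictor with an odds ratio of 2 per SD and k − 1 null; 1,500 datasets per setting; Wald tests at 0.05. The OR is the exponential of the mean coefficient. RMSE is for the log odds ratio. The last column is the chance that at least one null covariate has p < 0.05.

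| Rate | k | OR, ML | OR, Firth | RMSE, ML | RMSE, Firth | Any false predictor, ML / Firth |
|---|---|---|---|---|---|---|
| 0.35 | 3 | 2.19 | 2.03 | 0.391 | 0.338 | 8% / 5% |
| 0.35 | 5 | 2.25 | 2.03 | 0.396 | 0.323 | 18% / 12% |
| 0.35 | 8 | 2.38 | 2.04 | 0.463 | 0.337 | 34% / 20% |
| 0.35 | 10 | 2.53 | 2.06 | 0.538 | 0.351 | 40% / 20% |
| 0.25 | 3 | 2.17 | 2.00 | 0.416 | 0.357 | 10% / 8% |
| 0.25 | 5 | 2.30 | 2.04 | 0.480 | 0.377 | 18% / 12% |
| 0.25 | 8 | 2.49 | 2.05 | 0.587 | 0.396 | 32% / 19% |
| 0.25 | 10 | 2.57 | 2.01 | 0.637 | 0.385 | 40% / 21% |

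At a rate of 0.35, ML therefore inflates the odds ratio by about 10% with 3 covariates (2.19/2 = 1.095) and about 27% with 10 (2.53/2 = 1.265). The median ML estimates are less extreme: 2.13 with 3 and 2.39 with 10.

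**5. Source of the false predictors.** With 10 covariates there are 9 nulls. Independent tests at exactly 5% would give 1 − 0.95⁹ = 37%, against 40% observed under ML. With 3 covariates, 1 − 0.95² = 9.8%, against 8–10% observed. The ML error rate per null covariate at a rate of 0.35 is 4.2% with 3 terms and 6.3% with 10. Most of the 40% thus comes from the number of tests. Firth's lower figures arise partly because its Wald tests run below the nominal level here, at about 3% per null covariate.

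**The case against.** The strongest reply is that the Protocol does not contain the specification being criticised. It never calls the regression ordinary or unpenalised, and it gives no covariate count. The baseline visit list is a schedule of assessments, not a list of model terms, and the reference to models in the plural allows several small ones. With 3 terms the bias is only about 10% and the false-positive rate is nominal. Covariate choice is commonly settled in the SAP, which is not at hand. The count of 23 is inferred from a discordance probability, and the text does not say which of the Protocol's remission definitions the predictor model uses. General predictor modelling appears in none of the listed objectives, endpoints or outcomes; the nearest is the comparison across treatment lines.

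Much of this stands. A reader might infer that the plan is bound to produce inflated odds ratios and spurious predictors. The text does not support that, because the larger effects need a model with many terms, which the Protocol neither plans nor rules out. A reader might also infer that penalisation by itself cures false predictors. It does not: with 10 terms about a 20% chance remains. Nor does the Protocol give grounds for insisting on a particular number of terms or on particular ones.

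What survives is the choice of estimator. In the settings simulated, Firth's method is closer to the truth and has lower RMSE at every model size, including the smallest. The recommendation therefore holds whichever terms an SAP names, and no SAP can add remissions.

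**Conclusion.** The point holds as a minor improvement to a secondary analysis; it is not an error in the Protocol. On the plan's own inputs about 23 remissions are expected, or about 16 at the lower rate. Standard maximum likelihood then overstates a true odds ratio of 2 as about 2.2 with 3 to 5 covariates and about 2.5 with 10. The chance of at least one false predictor goes from about 8–10% to about 40% over the same range, mainly through multiplicity.

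This rests on four assumptions: unqualified logistic regression means maximum likelihood; 0.35 (or 0.25) approximates the Week 54 remission rate; about 65 patients are evaluable; and the covariates behave like independent normal variables. If enrolment followed the recomputed 52 evaluable patients, events would fall to 0.35 × 52 = 18.2.

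One further reading should be avoided. Predictors from this model might be taken to show who benefits from etrasimod. The Protocol describes an open-label study with no comparator arm, so the model can show only prognosis among treated patients.

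**What to change.** In the Statistical analysis section, state that the predictor model will be fitted by Firth penalised-likelihood logistic regression in R. Add that the terms will be chosen in advance and kept few relative to the expected remissions, and that results will be reported as exploratory prognostic associations with confidence intervals. The number and identity of the terms can go in the SAP.

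The cost is a change of wording and slightly more analysis work, with no extra patients, visits or data. The downsides are that fewer predictors are examined jointly and that Wald tests after Firth fitting are somewhat conservative, which is a further reason to emphasise intervals over p-values.

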Background Ulcerative colitis (UC) is a chronic inflammatory bowel disease characterized by relapsing and remitting inflammation of the colon [1]. Despite advancements in therapeutic options, including biologic agents and small molecules, many patients experience inadequate response, loss of response, or intolerance to existing treatments, especially after exposure to multiple biologics [2].

Etrasimod is a once-daily, oral selective sphingosine 1-phosphate (S1P) receptor modulator that primarily targets S1P1,4,5 with no detectable activity on S1P2,3, distinguishing it from first-generation S1P modulators associated with adverse effects [3]. By reversibly sequestering lymphocytes in lymph nodes, Etrasimod reduces peripheral immune cell trafficking to inflamed gastrointestinal tissue, thereby mitigating inflammation while maintaining immune surveillance [3,4]. This mechanism is particularly relevant for UC, as immune-mediated dysregulation contributes significantly to disease pathophysiology [4].

Recent phase 3 trials (ELEVATE UC 52 and ELEVATE UC 12) demonstrated that Etrasimod significantly improves clinical, endoscopic, and histologic outcomes in patients with moderate-to-severe UC, including those who have failed previous therapies [5]. The efficacy and tolerability of Etrasimod make it a promising oral alternative for patients requiring durable disease control without the burdens associated with parenteral biologic administration [5].

This study aims to prospectively evaluate the efficacy and safety of Etrasimod over one year in patients with moderate-to-severe UC who have previously been exposed to biologic therapies, further expanding the evidence for its real-world application and impact on symptom control, including urgency assessment through the validated Urgency Numeric Rating Scale (UNRS).

Study Design

• Type: Multicenter, Prospective, Open-Label Study

Duration: 54 weeks

- Population: Adults diagnosed with moderate-to-severe UC who have failed or are intolerant to at least one prior biologic therapy
- **Timeline:** Enrollment: July 2025 to December 2025; Treatment period: 54± 4 weeks for each participant; Data collection: as follows.

Objectives

Primary Objective:

• Evaluate the effectiveness of Etrasimod in achieving deep remission at Week 54, defined as the simultaneous presence of clinical and endoscopic remission.

Secondary Objectives:

- Assess the safety profile of Etrasimod over 54 weeks.

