 from baseline.

4. Endoscopic Response at 54 ± 4 weeks

 To evaluate the proportion of patients achieving endoscopic response at 54 ± 4 weeks, defined as at least a 1-point reduction from baseline in the Mayo endoscopic subscore.

5. Clinical Response at 12, 24 and 54 ± 4 weeks

 \circ To determine the proportion of patients achieving clinical response at 12, 24 e 54 \pm 4 weeks, defined as a decrease of at least 2 points and 30% from baseline in the 9-point MMS, with either a reduction of rectal bleeding subscore by at least 1 point or an absolute rectal bleeding subscore of 0 or 1.

6. Change in Fecal Calprotectin and C-Reactive protein from Baseline to 12, 24 e 54 ± 4 weeks

 \circ Biochemical response will be defined as either normalization (FC < 150 μg/g and CRP < 5 mg/L) or a ≥50% reduction from baseline values in patients with elevated biomarkers at study entry.

7. Change in Bowel Urgency Based on the Urgency NRS from Baseline to 12, 24 e 54 ± 4 weeks

 To evaluate changes in bowel urgency severity using the Urgency Numeric Rating Scale (NRS) at 12, 24 e 54 ± 4 weeks.

8. Comparing Effectiveness Across Different Treatment Lines by 54 ± 4 weeks

• To compare the efficacy of Etrasimod in achieving the primary study endpoint when used as a second, third, or fourth-line biological treatment.

9. Normalization of Bowel Wall Thickness (BWT) at 12, 24 e 54 ± 4 weeks (optional)

• To determine the proportion of patients exhibiting normalization of bowel wall thickness (BWT) on intestinal ultrasound (IUS), defined as a rectum ≤4.0 mm, sigmoid colon ≤4.0 mm, descending colon ≤3.0 mm, transverse colon ≤3.0 mm, and ascending colon ≤3.0 mm, at 12, 24 e 54 ± 4 weeks. This will be evaluated only in patients with increased BWT at baseline. [7,8]

10. Ultrasound Remission at 12, 24 e 54 ± 4 weeks (optional)

 To evaluate the proportion of patients achieving an intestinal ultrasound remission score of ≤6.2 based on the Milano Ultrasound Criteria (MUC) after 12, 24 e 54 ± 4 weeks of Etrasimod treatment. This will be evaluated only in patients with an MUC score >6.2 at baseline.

11. Deep Remission at 12, 24 e 54 ± 4 weeks

To assess the proportion of patients achieving deep remission at 12, 24 e 54 ± 4
weeks, defined as a rectal bleeding subscore of 0, a stool frequency subscore of 0,
and an eMayo score ≤1. [9]

12. Disease Clearance at 12, 24 e 54 ± 4 weeks

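### Student's t-test is planned for group comparisons with no unequal-variance form named; Welch's test would be a cheap, low-priority improvement for secondary comparisons

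*Protocol*

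**What the plan says.** The Statistical analysis section of the protocol fixes the test by name: "Between-group comparisons of continuous variables will be conducted using Student's t-test or Mann-Whitney U test, depending on data distribution". The only switch it gives is the shape of the data. Earlier in the same section it plans a variance check: "Normality will be assessed using the Kolmogorov-Smirnov test and Levene's test for homogeneity of variance". No consequence is attached to that check, and no unequal-variance test appears anywhere. The threshold is general: "A two-tailed p-value < 0.05 will be considered statistically significant".

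The design line reads "Multicenter, Prospective, Open-Label Study", and the Intervention section describes one regimen, so there is no control arm. The protocol does not say which groups the t-test line is meant for. The one group comparison it spells out, item 8 of the secondary outcome measures, is by treatment line: "To compare the efficacy of Etrasimod in achieving the primary study endpoint when used as a second, third, or fourth-line biological treatment". That outcome is binary.

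Other analyses have their own methods. For the primary endpoint: "To compare paired proportions (e.g., remission status at baseline vs Week 54), McNemar's test will be used". Repeated measures go to GEE, repeated-measures ANOVA or mixed models.

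**The concern.** Student's t-test ordinarily means the pooled-variance form. It tests equality of means and relies on equal variances as an assumption. In a randomised comparison with equal allocation that assumption matters little. Here any groups are subsets formed by outcome or history, and nothing makes them alike in size or spread.

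If the smaller group is the more variable, the pooled standard error is too small and the test rejects too often. If the smaller group is the less variable, the pooled standard error is too large and power is lost. The planned Levene's test shows that unequal variances were thought of, but as written it leads nowhere. At stake is the calibration of secondary or exploratory comparisons read at 0.05.

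**Working it through.** **Inputs from the protocol.** Two-sided alpha is 0.05. Sample Size Determination gives the headcount: "and a drop-out rate of 5%, is 68 pairs". 68 × 0.95 = 64.6, so about 65 completers. The protocol states no figure for the t-test comparisons, so there is none to reproduce. The 68 enters only as a headcount. Miettinen's formula with the stated inputs gives 51.7, so 52, or 55 after dividing by 0.95, not 68. That is a separate matter on which this point does not depend.

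**Assumed inputs.** The protocol gives neither group sizes nor SDs. I take normal data and SD ratios (smaller group to larger) of 0.5 to 2. For the split, the planning inputs are "power of 0.8, probabilities of discordant pairs 0–1 and 1–0 equal to 0.35 and 0.10 respectively".
- 0.35 × 65 = 22.75 gives 23/42. Entry requires an endoscopic subscore of at least 2 and deep remission requires at most 1, so nobody can be in deep remission at baseline. That makes 0.35 the planning figure nearest a Week 54 rate.
- (0.35 − 0.10) × 65 = 16.25 gives 16/49. This is a net change, not a stated remission rate, and serves only as a more extreme assumption.

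**Formula.** The true variance of the mean difference is V = s1²/n1 + s2²/n2. The pooled test estimates on average P = [(n1−1)s1² + (n2−1)s2²]/(n1+n2−2) × (1/n1 + 1/n2). With r = √(V/P) and a critical value of 1.998 on 63 degrees of freedom, approximate size is 2[1 − Φ(1.998/r)]. Approximate power at a true difference of 2.9√V is 1 − Φ(1.998/r − 2.9).

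**Smaller group with twice the SD, 23/42.** V = 4/23 + 1/42 = 0.1977. P = (22×4 + 41)/63 × (1/23 + 1/42) = 2.0476 × 0.0673 = 0.1378. r = 1.198, so size ≈ 2[1 − Φ(1.668)] = 9.5%.

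**Smaller group with half the SD, 23/42.** V = 0.25/23 + 1/42 = 0.0347. P = (22×0.25 + 41)/63 × 0.0673 = 0.0497. r = 0.836, so size ≈ 1.7% and power ≈ Φ(0.509) = 69%.

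**Simulation** (100,000 runs for size, 40,000 for power, power at a shift of 2.9 true standard errors):

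| Split | SD ratio, smaller:larger | Student size | Welch size | Student power | Welch power |
|---|---|---|---|---|---|
| 23/42 | 0.5 | 2.0% | 5.0% | 69% | 81% |
| 23/42 | 1 | 5.1% | 5.1% | 81.5% | 80.9% |
| 23/42 | 1.5 | 8.0% | 5.0% | – | – |
| 23/42 | 2 | 10.1% | 5.0% | – | – |
| 16/49 | 0.5 | 0.9% | 5.1% | 56% | 81% |
| 16/49 | 1 | 5.0% | 5.0% | 81.5% | 79.5% |
| 16/49 | 1.5 | 10.8% | 5.0% | – | – |
| 16/49 | 2 | 15.7% | 5.1% | – | – |
| 32/33 | 0.5 | 5.0% | 5.1% | 81% | 81% |
| 32/33 | 2 | 5.5% | 5.1% | 82% | 81% |

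Power is left out where Student's size is inflated, because the comparison would not be fair. The rows at ratio 1 and at 32/33 show that harm needs unequal sizes and unequal SDs together.

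**Do the planned checks repair it?** Levene's test detects a 1.5-fold SD difference in about 53% of runs at 23/42 and 46% at 16/49 (smaller group more variable). If rejection led to Welch, which the protocol does not say, overall size would be 5.3–6.1% at 23/42 and 6.2–7.5% at 16/49. In the reverse direction it would be about 4–5%. If the data went to Mann-Whitney instead, a ratio of 2 would still give about 8% at 23/42 and 10% at 16/49 with equal means.

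**The case against.** The strongest reply is that nothing important depends on this line. The primary endpoint uses McNemar, predictors use logistic regression, and repeated measures use GEE or mixed models. The UNRS section plans to correlate urgency with remission, which falls under Spearman. The treatment-line comparison has a binary outcome. The t-test sentence is a general provision with no named endpoint. This stands, and it sets the priority.

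Second, scores that pile up at a floor, such as urgency or biomarkers among remitters, are not normal, and the plan's own rule would normally send them to Mann-Whitney. That stands too: the figures above apply to approximately normal variables only.

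Third, Levene's test may be meant to lead to Welch, and an SAP that is not shown may say so. On that reading the remaining error is small, at most about 7.5% in the settings tried. But the protocol names the test and makes the choice depend on distribution alone, so the reading has to be supplied by the reader.

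A reader might also infer that unequal group sizes alone make the test reject at the wrong rate, or that equal variance is part of its null. Neither is right. With equal SDs Student's test holds 5% at every split tried, and equal variance is an assumption of the test, not what it is meant to detect.

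**Conclusion.** The point holds as a cheap improvement of low priority. The protocol names the pooled-variance test, runs a variance check that leads nowhere, and offers no unequal-variance test. If groups differ in both size and spread, size is about 2% to 10% at a 23/42 split and about 1% to 16% at 16/49, against a nominal 5%. When the smaller group is the less variable, power is about 69% against 81%, or about 56–57% against 81%. Welch's test stays at about 5% throughout.

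These figures rest on assumed splits, assumed SD ratios of 0.5 to 2 and normal data. It would be wrong to read the 16% as an expected false-positive rate. It needs the more extreme split, which is not a remission rate stated in the protocol, and it needs the smaller group to be the more variable. If the smaller group is remitters with compressed scores, the error runs the other way, towards lost power. Nor do the documents support any doubt about the primary result or the sample size on this ground.

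**What to change.** In the Statistical analysis section, replace Student's t-test by Welch's t-test (unequal variances) for two-group comparisons of approximately normal continuous variables. Do not use Levene's test to choose between tests. Keep Mann-Whitney for clearly skewed or ordinal variables, as the plan already does.

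The cost is one line of wording. When variances really are equal, Welch's test gives up at most about 2 points of power (79.5% against 81.5% at 16/49, and under 1 point at 23/42). No other analysis changes.
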